Early diagnosis and treatment based on subtype are recommended to halt progression of symptom severity [5]. Flushing is better prevented rather than treated, by avoiding specific triggers, decreasing transepidermal water loss by moisturizers, and blocking ultraviolet light [5]. Nonselective β -blockers and α 2-adrenergic agonists decrease erythema and flushing [5], while pulsed dye laser [5, 6] and intense pulsed light are used for telangiectasias [5]. Pulsed dye laser also addresses the diffuse erythema and enlarged pores characteristic of rosacea [6].

Oxymetazoline hydrochloride 1% cream (RHOFADE[™]) is a newly FDA-approved topical medication for adult rosacea patients. A primarily alpha-1a agonist, oxymetazoline hydrochloride (HCl) is thought to diminish erythema through vasoconstriction [7]. RHOFADE was evaluated for the treatment of persistent erythema associated with rosacea in two identical, randomized, double-blind, vehicle-controlled, parallel-group clinical trials [8]. A total of 489 subjects with persistent facial erythema associated with rosacea were treated with RHOFADE once daily for 4 weeks. An additional 440 subjects with persistent facial erythema associated with rosacea were also treated with RHOFADE once daily for up to one year in a long-term (open-label) clinical trial [8]. Disease severity was graded by the clinician using a 5-point clinician erythema assessment (CEA) scale [4] and by the subject on a similar 5-point subject self-assessment (SSA) scale, on which subjects scored either “moderate” or “severe” on both scales. Composite success, defined as the proportion of subjects achieving at least a 2-grade improvement on both CEA and SSA, was 15% in Trial 1 and 12% in Trial 2 on Day 29 of treatment [8].

Nonpurpuragenic pulsed dye laser (PDL) and intense pulsed light treatment have resulted in significant reduction in cutaneous erythema, telangiectasia and patient-reported associated symptoms of erythematotelangiectatic rosacea [9]. The PDL is an ideal energy-based device to treat the cutaneous vasculature of rosacea, since the 595nm wavelength is strongly taken up by the hemoglobin in blood vessels [6, 10]. With Vbeam 595nm PDL, ultra-long pulse durations reduce purpura while treating the telangiectasias associated with rosacea, which is more comfortable for patients [5, 6].

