The cutaneous manifestations of rosacea significantly impact patients’ well-being, social and emotional health [5], and alternatives to further improve management and treatment of this condition are necessitated.

The objective of this pilot study is to evaluate the efficacy of Rhofade topical drug therapy combined with Vbeam PDL treatment. The study hypothesis is that a synergistic approach to treatment may improve the treatment course by a mechanism of action in which oxymetazoline acts as a vasoconstrictor, slowing down vascular flow and allowing for occlusion with PDL to close off the vessels quicker.

 Candela Corporation Confidential	Pilot Study to Evaluate Combined Vbeam[®] Pulsed Dye Laser Treatment and RHOFAD[™] (oxymetazoline hydrochloride) Topical Cream for Erythematotelangiectatic Rosacea			
	Protocol #	DHF24671	Rev. Date	June 11, 2018

Study Device

The Candela Family of Pulsed Dye Laser Systems, including the 595nm pulsed dye laser wavelength, are FDA-cleared systems (K051359; K050673). The Vbeam 595nm PDL is indicated for treatment of benign cutaneous vascular lesions, benign epidermal pigmented lesions and periorbital wrinkles. The Vbeam is also indicated for treatment of inflammatory acne vulgaris.

The FDA-cleared Vbeam system includes spot sizes of 3, 5, 7, 10, 12 mm and 3x10 (elliptical). The study device is a modified version of the FDA-cleared system that includes an additional 15-mm spot size. The Vbeam and modified Vbeam are non-significant risk (NSR) devices. The modified Vbeam system provides epidermal cooling by either cryogen spray (Dynamic Cooling Device), as with the FDA-cleared system, or contact with a cooled window (termed contact-cooling). The modified Vbeam system (Vbeam Prima) recently received FDA clearance (K180593) on June 5, 2018.

Study Drug

RHOFAD[™] is an alpha_{1A} adrenoceptor agonist indicated for the topical treatment of persistent facial erythema associated with rosacea in adults [8].

There are no contraindications associated with topical use of RHOFAD[™] for the topical treatment of persistent facial erythema associated with rosacea in adults.

There are warnings and precautions associated with use of the 1% topical cream, as indicated in the FDA-cleared package insert. These include the following:

- Alpha-adrenergic agonists as a class may impact blood pressure.

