Comfort assessment will be performed independently by the subject using a numerical scale response (NSR) scale 0=No pain to 10=Worst possible pain (*Appendix III*). Subjects will be asked to fill out a questionnaire after each PDL treatment (Tx.1 – Tx.3).

Primary Efficacy Endpoint:

- Clinician erythema assessment (CEA): 5-point scale (0=Clear to 4=Severe) at 6-month follow-up compared to baseline.
- Subject self-assessment (SSA) 5-point scale similar to CEA at 6-month follow-up compared to baseline.

Secondary Efficacy Endpoints:

- Investigator and subject assessment of overall changes in skin condition (skin texture, vessel size, flushing), using a Global Aesthetic Improvement (GAI) 5-point scale (0=Excellent improvement to 4=No difference) – *Appendix IV, Table 4.*
- Investigator assessment of improvement in vessel size – *Appendix IV, Table 5.*
- Subject satisfaction 5-point scale (0=Very satisfied to 4=Very dissatisfied) – *Appendix IV, Table 6.*

Safety Endpoints:

- The number, severity and type of any adverse event recorded throughout the study and post-treatment (discomfort (pain), immediate and delayed response).
- Occurrence of expected post-treatment immediate response following each treatment based on a predefined scale (*Appendix IV, Table 3*).
- Discomfort (pain) level using a 10-point visual analog scale will also be recorded after each PDL treatment, using a Numerical Scale Response (NSR) – *Appendix III.*

Study Duration

The duration of the entire study from first subject enrollment to last subject completing the 6-month follow-up, is expected to be approximately 1 year.

Subject Population

Up to 60 healthy male and female adults (greater than 18 years of age), who meet the inclusion and exclusion criteria.

Subjects enrolled in the study can discontinue their participation at any time, for any reason, without prejudice or reduction in the quality of their medical care. In addition, the investigator or the sponsor can terminate a subject's participation in this study to protect the subject's health or if the subject is not compliant with the study protocol and schedule. Subjects may be replaced if withdrawn or lost from the study.

All subjects enrolled into this study must meet the following criteria:

Inclusion Criteria:

1. Subject is a healthy male or female of 18 to 75 years of age.

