Inclusion/ Exclusion Criteria	X				
Subject # Assignment	X				
Randomization to Study Arm	X				
Pregnancy Urine test	X				
Vbeam PDL test spots, (optional) – Arm 1	X	X		X	
Change to Medical History		X	X	X	X
Photographs, prior to any treatments		X	X	X	X
VISIA photographs, prior to any treatments (optional)		X	X	X	X
Clinician erythema assessment (CEA), prior to any treatments	X	X		X	X
Subject self-assessment (SSA), prior to any treatments	X	X		X	X
Vbeam PDL Treatment – Arm 1		X		X	
Tx Pain Assessment – Arm 1		X		X	
Immediate Treatment Response – Arm 1		X		X	

Visit	Screening /Baseline	Tx 1*/ 1-month FU	1-week (± 2 days) Safety Evaluation	Tx 2 - 3 / 2 & 3-Month FU Visits (4± 1 week)	6-Month (± 2 weeks) FU
Photographs, 10 mins post any treatment (optional) – Arm 1		X		X	
Global Aesthetic Improvement (GAI)		X		X	X
Vessel size assessment		X		X	X
Subject Satisfaction Questionnaire		X		X	X
Adverse Events and Serious Adverse Events	X	X	X	X	X
End of participation (Termination)					X

*For Arm 1, the 1st PDL treatment will be scheduled at approximately 4 weeks following the screening visit.

Screening Procedures

- A brief relevant medical history will be obtained to address inclusion/exclusion criteria for the study.
- Clinician erythema assessment (CEA) and subject self-assessment (SSA) will be obtained to address inclusion criteria for the study. Subjects with “moderate” or “severe” (Grade 3 or 4) are eligible for study participation (*Appendix II*).
- Pregnancy will be assessed for female subjects based on their last menstrual period, ability to become pregnant (surgical sterilization, birth control), and whether they have plans to become pregnant during the 6-month study period.
- The subject will undergo a standard skin exam to determine if they meet the study criteria.
- If the subject meets the criteria for the study, he or she will discuss with the study staff the study procedures, risks, benefits, and commitments associated with enrollment into the study. The staff will then review the consent form in detail with the subject, after which the subject will be given ample time to review the form. The subject will sign a consent form after the subject fully understands the possible risks/benefits of the study and wants to participate in study. The person conducting the session and the investigator will subsequently sign the consent form.

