- Once the consent form is signed, the subject will be assigned the next consecutive subject number and will be randomized to a treatment arm.
- Women capable of childbearing will undergo a urine pregnancy test.

- Skin type will be recorded using the Fitzpatrick Scale.
- Test spots may be performed (optional) for subjects in Arm 1 to determine the subject's response to selected treatment parameters. Test spot locations will be selected by the investigator.
- Subjects in Arms 1 & 2 will be provided with RHOFADE topical cream and instructed to apply once daily, according to the drug insert instructions: apply a pea-sized amount once daily in a thin layer to cover the entire face (forehead, nose, each cheek, and chin) avoiding the eyes and lips.
- The RHOFADE topical cream will be applied daily for 4 weeks prior to the first PDL facial treatment.
- Subjects must discontinue topical use for a 3-day washout period prior to each PDL treatment.

Pre-Treatment PDL Care

In order to minimize pain during laser irradiation, subjects will be offered to use topical anesthetic cream (EMLA), which will be applied to the skin surface 30-60 minutes prior to laser irradiation.

PDL Treatment Procedure

- Treatments will be performed every 4 (± 1) weeks. Subjects in Arm 1 must discontinue topical use for a 3-day washout period prior to each PDL treatment.
- Laser treatment procedures will conform to all laser safety instructions and should be conducted per the procedure described.
- The investigator, all personnel in the treatment room and the subject will wear protective eyewear, appropriately rated for the device wavelength(s) being operated.
- Based on the subject's response to the test spot evaluation (optional) or experience from treatment of prior subjects in this study or in practice, the investigator will select the parameters used for treatment, based on the threshold for nonpurpuragenic settings.
- Parameters include choice of: the 12 mm or 15 mm spot size, the laser fluence, the duration of the laser pulse exposures and the cooling procedure. The investigator will treat the face with the parameters chosen and will document the parameters.
- The treatment area will be photographed before each treatment and at each post-treatment follow-up visit. Optional photography can include photos at 10 minutes (approximately) after each treatment.
- All subjects will be treated as follows:
 - The 12 mm or 15 mm spot size will be used.

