 - Treatment pulses will be delivered at the threshold for nonpurpuragenic settings.
- Subjects will be instructed to report any discomfort and/or comments during and post treatment. Discomfort will be rated on a scale from 0 = no pain to 10 = worst imaginable pain using the NRS scale (*Appendix III*).
- Immediate clinical response post-treatment will be recorded for: purpura, edema, erythema, and blistering, based on a predefined scale (*Appendix IV, Table 3*).
- Post-treatment photographs (optional) may be taken, approximately 10 mins post treatment, to document post treatment effects such as the collapse of blood vessels, or to document post treatment purpura, erythema, etc.

- Subjects will be instructed on post-treatment care, including the use of sunscreen.
- Subjects in Arm 1 will apply RHOFADE topical cream immediately (in-office) following the PDL treatment. If subjects find it irritating to the skin to apply Rhofade immediately after PDL treatment, then they may apply it within 24 hours of subsequent treatments.

1-Week Post-Treatment 1 Safety Evaluation:

Subjects in Arm 1 will be scheduled for a 1-week (± 2 days) safety evaluation following the first PDL treatment. The following procedures will be conducted during this visit:

- A brief relevant medical history review for any changes from baseline.
- Skin evaluation of treatment area.
- Photographs of treatment area.
- Adverse event reporting.

Follow-up Study Visits:

The following procedures will be conducted during the 1-, 2-, 3- and 6-month study visits for subjects in both Arms 1 & 2:

- A brief relevant medical history review for any changes from baseline.
- Skin evaluation of treatment area.
- Photography will be performed according to the same procedure used at the baseline visit.
- VISIA photography (optional) may be performed according to the same procedure used at the baseline visit.
- Clinician erythema assessment (CEA) and subject self-assessment (SSA) will be recorded prior to treatment (*Appendix II*).
- Assessment of improvement (pretreatment) will be recorded by the investigator and subject using the Global Aesthetic Improvement Scale (GAI) —*Appendix IV, Table 4*.
- Improvement in vessel size will be evaluated by investigator—*Appendix IV, Table 5*.
- Subject satisfaction will be reported —*Appendix IV, Table 6*.
- Treatment will be performed (Arm 1).

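### The 6-month CEA and SSA are scored without fixing, or requiring a record of, the time since the last cream application

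*Combined protocol and SAP*

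**What the plan says.** The primary efficacy endpoint has two parts: "Clinician erythema assessment (CEA): 5-point scale (0=Clear to 4=Severe) at 6-month follow-up compared to baseline" and "Subject self-assessment (SSA) 5-point scale similar to CEA at 6-month follow-up compared to baseline". The primary objective also compares Arm 1 (cream plus PDL) with Arm 2 (cream alone) at that visit.

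On the cream, Screening Procedures has both arms "instructed to apply once daily, according to the drug insert instructions". The protocol then gives the amount and the area of the face, but no time of day and nothing about visit days. The Background says that the drug "is thought to diminish erythema through vasoconstriction", and the study hypothesis again relies on the statement that "oxymetazoline acts as a vasoconstrictor".

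The only instruction to stop the cream is tied to the laser: "Subjects must discontinue topical use for a 3-day washout period prior to each PDL treatment". (The synopsis gives 2 days before the first session; the two statements need reconciling.) Study Design has Arm 1 on daily cream throughout the study apart from those wash-outs, and Arm 2 on continuous daily cream up to the 6-month visit. Table 2 schedules no PDL at 6 months.

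On the timing of scores, Table 2 has the row "Clinician erythema assessment (CEA), prior to any treatments", with a matching row for SSA; both are marked in the 6-month column. Follow-up Study Visits says "Clinician erythema assessment (CEA) and subject self-assessment (SSA) will be recorded prior to treatment". Neither Table 2 nor the visit lists include time of last application, a diary or a check of cream use.

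**The concern.** A vasoconstrictor changes the quantity that CEA and SSA measure, and a wash-out of days before PDL suggests that the protocol regards its effect as temporary. As written, one subject may be scored soon after a morning application and another nearly a day after the previous one. Their grades are then taken under different conditions but analysed as one measurement.

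Baseline is scored before cream is dispensed, so the change from baseline and the between-arm contrast both depend on the condition at 6 months. If application times vary at random, the cost is precision. If they differed by arm, the contrast would no longer isolate what PDL adds. Since the protocol asks for no record of the interval, the analyst may be unable to tell which happened or to adjust for it. The Photographs section has the same gap: it standardizes camera, position and lighting, but not time since application.

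**Working it through.** **What is fixed at the 6-month visit**

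| Item | Arm 1 | Arm 2 |
|---|---|---|
| Cream instruction | daily; wash-out only before PDL | daily, up to the visit |
| PDL at this visit | none | none |
| Wash-out before this visit | none | none |
| Hour of application | not stated | not stated |
| Interval to scoring | not stated | not stated |
| Record of last application | not required | not required |

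The instructions are equivalent in the two arms. What is missing is the interval.

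**Does the Table 2 timing rule close the gap?** If its treatments mean PDL, the rule has no effect at 6 months. If they include that day's cream, scoring comes first, but the hour of the previous day's dose is still open. Follow-up Study Visits favours the PDL reading, since its list goes on to performing treatment in Arm 1. The two sites could read the rule differently.

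**Inputs for size.** The protocol states no test, alpha, power, SD or allocation ratio, so there is no figure of its own to reproduce. All of these are assumptions except the maximum of 60 subjects:
- 30 per arm (an equal split of 60), two-sided 5% test, normal approximation.
- SD of CEA change at a common interval: 0.8 to 1.0.
- Difference *d* between a fresh and a worn-off score: 0.5 to 1.0 grade. It could be 0 if the effect lasts the whole day.

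SE = SD × √(2/30), which is 0.207 to 0.258. The difference detectable with 80% power is (1.960 + 0.842) × SE = 0.58 to 0.72 grade.

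**Noise, with the same mix in both arms.** A 50/50 mix is the worst two-point case. It adds 0.25*d*² to the variance, so SD′ = √(SD² + 0.25*d*²). Power for an assumed true difference of 0.7 grade:

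| SD | *d* | SD′ | Power at common interval | Power with mix |
|---|---|---|---|---|
| 0.8 | 0.5 | 0.838 | 0.92 | 0.90 |
| 0.8 | 1.0 | 0.943 | 0.92 | 0.82 |
| 1.0 | 0.5 | 1.031 | 0.77 | 0.75 |
| 1.0 | 1.0 | 1.118 | 0.77 | 0.68 |

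The loss is about 2 to 10 percentage points, and 0 if *d* = 0.

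**Bias, only if the mix differs by arm.** Bias = (difference between arms in the share scored on drug) × *d*.

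| Difference in share | Bias (grades) | Chance of rejection with no PDL effect |
|---|---|---|
| 0 | 0 | 0.05 |
| 25 points | 0.25 × 0.5 to 0.25 × 1.0 = 0.125 to 0.25 | 0.08 to 0.23 |
| 50 points | 0.50 × 0.5 to 0.50 × 1.0 = 0.25 to 0.50 | 0.16 to 0.68 |

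Nothing in the documents points to any row other than the first.

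**The case against.** **Arm 1 is told to be on cream.** A reader might infer that Arm 1, having stopped the cream before its visits at months 1, 2 and 3, will arrive off cream at 6 months and bias the contrast against PDL. The documents do not support that. Study Design instructs Arm 1 to apply daily through the study and ties the wash-out to PDL sessions only. By 6 months Arm 1 should have had two months (synopsis) or about three (Table 2 schedule) of uninterrupted use. A carried-over habit is conceivable but conjectural. Supervised applications after PDL could equally improve Arm 1's adherence. This part of the objection stands.

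**Application hours should balance under randomization.** This is a fair expectation, but it answers bias, not noise.

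**The noise is modest, and scoring under ordinary use is a legitimate pragmatic choice in a pilot.** The loss is indeed modest on the assumed inputs. But the protocol does not say that it has made that choice, and even a pragmatic design gains from recording the interval.

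**The case report form and drug insert are not in the documents.** This is true, so it cannot be said that nothing will be recorded or that the insert is silent on timing. What can be said is that the protocol requires no record and does not link scoring to application.

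**Months 2 and 3.** There Arm 1 is scored after a planned wash-out and Arm 2 on cream. That imbalance is built in, but it affects the secondary comparisons and is a separate matter. It should not be read across to the primary visit.

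**Conclusion.** The point holds as a gap in how the primary measurement is specified: the protocol neither fixes nor requires recording of the time from last application to the 6-month CEA and SSA, although the drug acts on what they score. The likelier consequence is lost precision: on the assumptions above, about 2 to 10 points of power at worst, and none if the effect does not fade within a day. Bias between arms is possible but not built in. It runs from 0 upward, and neither the wear-off nor any difference between arms can be estimated from the documents. The point does not undermine the design; the change is worth making because it is cheap and because application times not noted at the visit cannot be reliably recovered later.

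**What to change.** 1. State one common condition for 6-month scoring and photographs in both arms: the same interval since last application, chosen by the sponsor.
2. Reconcile that condition with the Table 2 timing rule, and say whether treatments there means PDL only or also that day's cream.
3. Remind Arm 1 before the 6-month visit that, under the protocol's own schedule, the wash-out is tied only to PDL sessions.
4. Add the date and time of last application to the visit record at each CEA/SSA.
5. Pre-specify a sensitivity analysis of the 6-month comparison in all randomized subjects, for example adjusted for time since application. That time arises after randomization, so the analysis supports the primary comparison and does not replace it. Label any analysis restricted to subjects within the interval as selected on post-randomization behaviour.

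The cost is a sentence or two in the visit procedures, an appointment reminder, one date-and-time entry per visit and less flexible timing of the 6-month appointment. The once-daily regimen is unchanged.

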After treatment, no special care is usually necessary for the treatment site. Aquaphor (similar to Vaseline) may be supplied to the subject to be applied to any area that feels irritated. The subject will also be instructed to apply cool compresses if they have any areas of swelling after treatment and to wash the treated area with soap or a gentle cleanser as they normally would for the week following treatment. The subject will be able to continue with their preferred routine skin care, excluding any method of wrinkle removal, the day after treatment. Sunscreen should be worn.

Data Recording

All data will be recorded in source documents and transcribed onto Case Report Forms (CRFs). Site will be monitored by Syneron staff or designees to assure adherence to the clinical trial requirements, subject safety, protocol procedures, and for data accuracy. The Case Report Forms and images will be reviewed and retrieved during the monitoring visit. All source documentation will remain in the subject's files at the site.

Protocol Revisions and/or Deviations

With the exception of emergency situations, no changes or deviations in the conduct of this protocol will be permitted without the prior approval of the sponsor.

The IRB/IEC that granted original approval for the study must be notified of all changes in the protocol and will approve any change or deviation that may increase risk to the subject, and/or that may adversely affect the rights of the subject or validity of the investigation.

 Candela Corporation Confidential	Pilot Study to Evaluate Combined Vbeam[®] Pulsed Dye Laser Treatment and RHOFADE[™] (oxymetazoline hydrochloride) Topical Cream for Erythematotelangiectatic Rosacea			
	Protocol #	DHF24671	Rev. Date	June 11, 2018

In the event of an emergency, the Investigator will institute any medical procedures deemed appropriate. However, all such procedures must be promptly reported to the sponsor and the IRB/IEC.

ADVERSE EVENTS (AE)

An adverse event (AE) is any adverse change in health or side effect that occurs in a study participant during their participation in the study.

Anticipated Adverse Effects

Anticipated adverse effects of laser-based treatments include: hyperpigmentation, blistering, crusting, bruising, scabbing, scarring, hypopigmentation, infection, and pinpoint bleeding. While unlikely, some adverse events may be permanent.

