An adverse event (AE) is any undesired clinical occurrence in a study subject as indicated by signs, symptoms, illnesses, events that develop or worsen in severity in association with the study when deemed by the Investigator to be related to use of the device or study procedures. The Investigator will document all adverse signs and symptoms regardless of severity or frequency that are either volunteered by subjects or observed during the course of the study that are related to the device. The Investigator will also record adverse experiences of subjects resulting from concurrent illnesses, reactions to concurrent medications, or progression of disease states that the Investigator deems related to the device. Included in the description will be the nature of the sign or symptom, the date of onset, whether the event was serious, the severity, the relationship to study procedures or investigational device, the action taken, the date of resolution, and the outcome. The Principal Investigator will then determine the relationship of the adverse device effect to the investigational device.

Unanticipated Adverse Device Effects

For device studies, part 21 CFR 812.3(s) uses the term unanticipated adverse device effect which is defined as any serious adverse effect on health or safety or any life-threatening problem or death caused by, or associated with, a device, if that effect, problem, or death was not previously identified in nature, severity, or degree of incidence in the investigational plan or application (including a supplementary plan or application), or any other unanticipated serious problem associated with a device that relates to the rights, safety, or welfare of subjects.

An unanticipated adverse effect will be graded as follows:

Mild: Sign or symptom, usually transient, non-life-threatening requiring no special treatment and generally not interfering with usual activities.

Moderate: Sign or symptom, non-life-threatening which may be ameliorated by simple therapeutic measures and may interfere with usual activity.

Major: Sign or symptom that is intense or debilitating but non-life-threatening and that interferes with usual activities. Recovery is usually aided by therapeutic measures and the discontinuation of the study device may be required.

Severe: Any untoward medical occurrence that at any time results in death or life-threatening illness, resulting in persistent or significant disability/incapacity.

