The relationship of the adverse effect to the study is defined as follows:

Probable: An adverse event has a strong temporal relationship to study device, and another etiology is unlikely or significantly less likely.

Possible: An adverse event has a strong temporal relationship to the study device, and an alternative etiology is equally or less likely compared to the potential relationship to study device.

Probably not: An adverse event has little or no temporal relationship to the study device and/or a more likely alternative etiology exists.

Not related: An adverse event has no temporal relationship to study device or has a much more likely alternative etiology.

Reporting Adverse Events (AE) and Serious Adverse Events (SAE)

The Investigator must report all unanticipated adverse device effects that are serious in nature to the clinical study monitor immediately or within twenty-four hours by telephone (see below). If such an unanticipated adverse device effect is reported after normal working hours, the Investigator will leave a voice message at the monitor's telephone number with accompanying report of the unanticipated adverse device effect faxed or sent to the fax number/e-mail address below:

[name], Global VP of Clinical and Regulatory Affairs

Telephone Number (mobile): [contact]

Email: [contact]

A written report prepared by the Principal Investigator must follow within five working days to both the IRB and to Candela and should include a full description of the event and sequence.

MEASURES TAKEN TO PROTECT THE RIGHTS AND WELFARE OF SUBJECTS

Research records will be available to study personnel, and the Institutional Review Board, where applicable. Research records may be used for purposes of medical education, after removal of patient names or other identifying information. Subjects will be required to provide permission for the

 Candela Corporation Confidential	Pilot Study to Evaluate Combined Vbeam[®] Pulsed Dye Laser Treatment and RHOFADÉ™ (oxymetazoline hydrochloride) Topical Cream for Erythematotelangiectatic Rosacea			
	Protocol #	DHF24671	Rev. Date	June 11, 2018

photographs taken of the treatment area during the study to be made available to the investigator and the sponsor for research and marketing purposes, after removal of identifying information. These photographs may be used for lectures, presentations or publications.

RISK/BENEFIT ANALYSIS

Risks

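### The protocol gives two conflicting AE definitions, and its recording duty, causality grades and 24-hour rule name only the laser, so cream reactions have no clear place in the safety record

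*Combined protocol and SAP*

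**What the plan says.** The section on adverse events opens by defining an AE as "any adverse change in health or side effect that occurs in a study participant during their participation in the study". The paragraph after the list of anticipated laser effects defines the term again: an event is an AE "when deemed by the Investigator to be related to use of the device or study procedures".

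That paragraph then sets the duty to document. The investigator records signs and symptoms "either volunteered by subjects or observed during the course of the study that are related to the device". A further sentence covers concurrent illness, reactions to concurrent medication, and "progression of disease states that the Investigator deems related to the device". Its closing condition can be read as applying to all three items or only to the last.

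The described AE record includes "the relationship to study procedures or investigational device". The paragraph ends: "The Principal Investigator will then determine the relationship of the adverse device effect to the investigational device".

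Four causality grades follow the subsection on unanticipated device effects. Their lead-in speaks of relationship to the study, but each grade is worded by the device. *Probable*, for example, begins: "An adverse event has a strong temporal relationship to study device, and another etiology is unlikely".

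Under the heading on reporting AEs and SAEs, the expedited rule reads: "The Investigator must report all unanticipated adverse device effects that are serious in nature to the clinical study monitor immediately", or within 24 hours by telephone.

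Other sections look wider. The synopsis makes the number, severity and type of AEs an endpoint in both arms, and the Safety Endpoints list in the body is not limited by product. Table 2 marks AEs and SAEs at every visit. Follow-up Study Visits lists AE reporting for both arms at months 1, 2, 3 and 6.

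**The concern.** Both arms use the cream and only Arm 1 receives the laser. The safety comparison is interpretable only if the same event is recorded and attributed by the same rule in each arm. An AE section built around the device cannot ensure that, because one arm never meets the device.

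Cream reactions are foreseen. The Study Drug section lists application-site dermatitis, pruritus, pain and erythema, and worsening inflammatory lesions, at 2% to 3% each over one year in an open-label trial. It also carries drug warnings, including effects on blood pressure and acute narrow-angle glaucoma.

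Three things are at stake: whether the two sites record the same events, whether a like reaction gets a like causality grade in each arm, and whether the protocol states an expedited route for a serious event due to the cream.

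**Working it through.** The plan gives no figure on this point and no arithmetic applies. The check sets each AE rule against three test events.

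| Text | Cream reaction, Arm 2 | Cream reaction, Arm 1, soon after laser | Event unrelated to either product |
|---|---|---|---|
| Opening definition | AE | AE | AE |
| Second definition | AE only if cream use counts as a study procedure | AE on the same basis, or if deemed device-related | Not an AE |
| Duty to document | Outside it | Inside only if deemed device-related | Outside it |
| Relationship field | Only through procedures | Device or procedures | Can be entered as neither |
| Principal Investigator's decision | Device only | Device only | Device only |
| Four causality grades | *Probably not* or *Not related* | *Possible* or *Probable* also available | *Probably not* or *Not related* |
| 24-hour rule, if serious | Not covered | Only if an unanticipated device effect | Not covered |
| Safety endpoints | Counted once recorded | Counted once recorded | Counted once recorded |

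1. **Definitions.** They disagree on the unrelated event under any reading. They disagree on the Arm 2 cream reaction unless cream use is a study procedure.

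2. **Duty to document.** The second definition admits the device or study procedures. The recording sentence that follows drops procedures and keeps only the device. Even on the generous reading of the definition, the cream reaction falls outside this sentence.

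3. **Grades.** All four of the four grades refer to the study device and none names the cream. Arm 2 has no laser, and the optional test spots are for Arm 1 only, so no Arm 2 event can have a strong temporal relationship to the device. The two upper grades are therefore closed to it. In Arm 1 the cream is applied in the office straight after each laser session, or within 24 hours of later sessions if it irritates. An investigator who cannot separate the two causes may grade the same reaction *Possible* or *Probable*. If the investigator judges the cream the more likely cause, the wording of *Probably not* applies in Arm 1 as well, so the difference between arms is possible rather than automatic.

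4. **Expedited reporting.** The heading covers AEs and SAEs, but the rule beneath it, and the written report due within five working days, are framed around serious unanticipated device effects.

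5. **Endpoint.** It counts AEs that are recorded, in both arms. It therefore inherits whichever recording rule a site applies.

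**The case against.** The strongest reply is that the cream already comes in through study procedures. Screening Procedures includes supplying it to both arms with instructions for daily use. The treatment and follow-up procedure lists include in-office application in Arm 1. On that reading a cream reaction meets the second definition, and the relationship field can carry it. The two definitions would then differ mainly on unrelated events. This is a fair reading and it narrows the point. It does not reach the recording sentence, the Principal Investigator's decision, the grades or the 24-hour rule, none of which mentions procedures.

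A second reply is that the grades are introduced as relationship to the study and follow the subsection on device effects, so they may belong to that subsection alone. The placement makes this arguable. However, each grade speaks of an adverse event, and if they do cover device effects only, the protocol states no causality scale for cream events.

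A third reply is that the endpoints, the visit schedule and the visit procedures all show an intent to capture AEs in both arms. That stands as intent, and it is why the point is one of conflict and risk.

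Three stronger inferences are tempting, and the documents do not support them:

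- A reader might infer that cream reactions will be lost, or that one arm will look safer. The broader texts may govern in practice, and no size or direction of bias can be shown.
- A reader might infer that the data forms have no place for the cream. The CRFs are not visible, so only the fields that the protocol describes can be checked.
- A reader might infer that a serious cream event has no reporting route at all. Protocol Revisions and/or Deviations requires prompt reporting of emergency medical procedures, with no limit by arm or product, and sponsor procedures and GCP are cited but not visible. What is missing is a stated expedited rule in this protocol for serious events not attributed to the device.

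**Conclusion.** The concern holds as a conflict of wording that should be fixed. Two AE definitions stand under one heading with no order of precedence. The recording sentence, the Principal Investigator's decision, four of four causality grades and the only 24-hour rule refer to the device alone. No AE field that the protocol describes names the cream.

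Taken literally, this conflicts with an endpoint of any AE in both arms. An Arm 2 cream reaction could be left out, or else graded as unlikely to be related or unrelated although the cream is that arm's only study treatment. The same reaction in Arm 1 could receive a higher grade.

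Confidence is high on the wording and low on whether events would in fact go unrecorded. The extent of under-recording cannot be estimated from the documents and may be none. The conclusion on grading assumes that the four grades apply to all AEs. The conclusion on the described fields is subject to the unseen CRFs.

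**What to change.** - Use the opening definition as the only AE definition. Remove the relatedness conditions from the second definition and from both recording sentences, so that all AEs are recorded in both arms.
- Record relatedness separately for the device, the cream and the study procedures. Reword the Principal Investigator's decision and the four grades to match.
- State that AEs are summarised by randomised arm.
- Reconcile the reporting text with its own AE and SAE heading, so that it covers serious events in either arm.

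The cost is protocol and CRF wording, relatedness fields for cream and procedures if the forms lack them, and possibly more AEs recorded. No visit, assessment or subject is added.
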